3.8.2 Assignment of AEs to Vaccination Period

Each AE will be assigned to a vaccination period using date and time of vaccination and date and time of start of AE. If not specified otherwise all AE tables will be presented divided into the following vaccination periods:

For Group 1:

- Vaccination Period 1 covers from Visit 1 (immediately after the first vaccination) until Visit 4 (just before the second vaccination).
- Vaccination Period 2 covers from Visit 4 (immediately after the second vaccination) until Visit 7 (just before the third vaccination).
- Vaccination Period 3 covers from Visit 7 (immediately after the third vaccination) until Visit 10.
- The Overall MVA-BN[®] Vaccination Period is the combination of Vaccination Periods 1 and 2.

For Group 2:

- Vaccination Period 1 covers from Visit 1 (immediately after the first vaccination) until Visit 4.

If start time is missing and start date of AE coincides with the date of a vaccination, the AE will be assigned to the vaccination period corresponding to the vaccination on this date.

Each AE starting at or after first vaccination not matching the definition of a solicited AE is defined as an unsolicited AE. If a solicited AE begins outside of the 15-day window following the last vaccination it will be considered an unsolicited AE regardless of the preferred term. If start time is missing and start date coincides with date of current vaccination, it will be regarded as a treatment emergent AE. If the start date is (partially) missing the AE will be regarded as a treatment emergent AE following the worst case principle. If the AE cannot be assigned to a vaccination period 1 or 2 because of a (partially) missing start date it will be assigned to the overall MVA-BN[®] vaccination period (Group 1). If the AE cannot be assigned to vaccination period 2 or 3 then it will not be assigned to a vaccination period. AEs which cannot be assigned

to a vaccination period will still be included in per subject based tables and in the listings (with partial dates).

AEs with onset after the active trial phase will be considered to fall within the FU phase.

3.8.3 General Considerations for AEs

MedDRA (Medical Dictionary for Regulatory Activities) version 18.0 will be used for coding of AEs.

Duration of an AE is calculated as follows:

Unsolicited AE: expressed in [days]

- end date of AE – start date of AE + 1
- in case of (partially) missing start date and/or (partially) missing end date imputed dates will be used in the calculation.
- in case the AE is ongoing at the end date, the duration will not be calculated

Solicited AEs: expressed in [days]

- end date of AE – start date of AE + 1 where end date is the last day the symptom is defined as an AE and start date is the first day symptom is defined as an AE (no matter if the AE occurred at every day between first day and last day).
- in case the AE is ongoing at the end date, the duration will not be calculated

Time interval between vaccination and start of AE are calculated as follows:

Relative day of start of AE is calculated as follows:

Unsolicited AEs: expressed in [days]

- start date of AE – date of vaccination of the corresponding period
- in case of (partially) missing start date no calculation will be done.

Solicited AEs: expressed in [days]

- start date of AE – date of vaccination of the corresponding period where start date is the first day a symptom is defined as an AE, and vaccination day corresponds to the day of vaccination for each period.

Local and General Unsolicited AEs

Any unsolicited AE which is recorded with the preferred term including the text “injection site” or “vaccination site” will be considered as a local reaction. Any other preferred terms which are

considered as local events will be documented in the DRM minutes. Any unsolicited AE not classified as a local AE will be classified as a General AE.

All available safety data collected during the FU phases will therefore be simply listed. However the new onset SAEs reported during the FU phase will be analyzed.

3.9 Analysis Variables

3.9.1 Demographic and Other Baseline Characteristics

Demographics

- Age (years)
- Age bands (15-24 years, 25-34 years, 35-44 years)
- Gender
- Race (American Indian or Alaskan Native, Oriental/Asian, Black/ African American, Native Hawaiian / Other Pacific Islander, White/Caucasian, Other)
- Ethnicity (Hispanic or Latino, or Non-Hispanic or Latino)
- Height [cm]
- Body weight [kg]
- Body Mass Index (BMI)

Other Baseline characteristics

- History of smallpox vaccination or vaccination with other pox-virus based vaccine
- Medical history (including cardiac risk assessment)
- Baseline signs and symptoms pre-existing to vaccination

3.9.2 Safety Variables

Physical examination (complete examinations at Visit SCR and targeted physical examination at other visits).

Only abnormal physical examination results will be listed.

Vital signs (at each visit)

- Heart rate [beats per minute]
- Systolic and diastolic blood pressure [mmHg]
- Body temperature [°F]
- Respiratory rate (breaths/min)

12-lead electrocardiogram (ECG) (at SCR and Visit 3 and in Group 1 only Visit 9)

(Additional ECGs will be performed and reported if clinically indicated [e.g. in Group 1 at Visit 6], or in case of any clinically significant cardiac events are present)

- Investigator's overall interpretation (normal, abnormal)
- Clinical significance

Safety laboratory data (at SCR, Visit 3 and in Group 1 only Visit 6 and Visit 9)

Clinical chemistry (serum)

- Total bilirubin
- Alkaline phosphatase
- SGOT/AST (Aspartate Aminotransferase)
- SGPT/ALT (Alanine Aminotransferase)
- Serum creatinine
- Sodium
- Potassium
- Calcium
- Troponin I (at SCR and Visit 3 and in Group 1 only Visit 9)

And the following only at SCR

- LDL
- HDL
- Hepatitis B/C –Testing
- HIV Testing
- Total cholesterol

Hematology (whole blood)

- Red blood cell count
- Hemoglobin
- Total and differential WBC (Eosinophils, Basophils, Neutrophils - % and absolute -, Leucocytes, Lymphocytes, Monocytes)
- Platelet count

Pregnancy test (serum β -HCG pregnancy test at SCR or urine β -HCG pregnancy test within 24 hours prior to each vaccination and at last active trial visit for women of childbearing potential.

Results of all pregnancy tests will be listed.

Solicited local AEs reported in the subject memory aid (on days of vaccination and during the following 14 days)

- Injection Site Erythema (Redness)
- Injection Site Swelling
- Injection Site Pain
- Injection Site Induration
- Injection Site Itching (Pruritus)

And vaccination site appearance (normal/healed, red spot, bump, reddish blister, whitish blister, scab, ulcer/crater, warmth, swollen >3inch, red streaks, drainage)

Solicited general AEs reported in the subject memory aid (on days of vaccination and during the following 14 days)

- Body Temperature (Fever)
- Headache
- Myalgia (Muscle pain)
- Chills
- Nausea
- Fatigue
- Malaise
- Swollen Lymph nodes (Lymphadenopathy)

Unsolicited AEs reported (on days of vaccination and during the following 28 days)

- Other, unsolicited local and general adverse events following vaccination

SAEs

AESI

In case any AESI is also an SAE it will be treated and reported as an SAE.

Prior and Concomitant medication

Assessment of ACAM2000[®] Vaccination Site

The following four measures will be derived from the subject's memory aids:

- healing time measured in days

- maximum lesion diameter measured in mm
- maximum erythema measured in mm
- maximum induration measured in mm

The following measurements will be made by the investigator at Day 0, Day 7, Day 14 and Day 28 visits following ACAM2000[®] vaccination

- lesion erythema measured in mm
- lesion induration measured in mm
- general appearance of the lesion

3.9.3 Immunogenicity and Efficacy Variables

Seropositivity (yes/no) at all sampling visits

- Vaccinia-specific neutralizing antibodies (PRNT)
- Total vaccinia-specific antibodies (ELISA)

Seroconversion (yes/no) at all post baseline sampling visits

- Vaccinia-specific neutralizing antibodies (PRNT)
- Total vaccinia-specific antibodies (ELISA)

Antibody titers at all sampling visits

- Vaccinia-specific neutralizing antibodies (PRNT)
- Total vaccinia-specific antibodies (ELISA)

The following assessments will be made using the SilhouetteConnect camera system (using the area perimeter drawn on the photograph)

- Lesion area at Day 6-8
- Lesion area at Day 13-15
- Lesion diameter at Day 6-8
- Lesion diameter at Day 13-15

The lesion area measurements will be confirmed by the blinded ITRC. Where there is a discrepancy, then the ITRC would have the final decision.

The following assessments will be made by the investigator

- Lesion diameter at Day 6-8
- Lesion diameter at Day 13-15
- Healing of lesion assessed at visits on Day 7, Day 14 and Day 28.

- Major erythema at Day 6-8
- Major erythema at Day 13-15
- Major induration at Day 6-8
- Major induration at Day 13-15

The following assessment will be made by the blinded ITRC:

- ITRC classification of lesion site (full take, partial take, absent take)
- MLA

3.9.4 Pharmacokinetic Variables

Not applicable

3.9.5 Pharmacodynamic Variables

Not applicable

3.10 Analysis and Presentation Methods

3.10.1 Listings and Descriptive Statistics

All individual data entered in the eCRF and derived data will be listed as measured in the Individual Subject Data Listing.

For ELISA and PRNT titers descriptive statistics will be based on Geometric Means and confidence intervals (CI). For other, continuous parameters, measurements will be summarized by means of descriptive statistics (i.e. number of observations (N), mean, SD, minimum (Min), median, maximum (Max)) and categorical data will be summarized by means of frequency tables (i.e. count and percentages) and CI, if not stated otherwise.

All tables and listings will be sorted by scheduled visit (and subject, if appropriate).

All tables will be presented split by treatment groups (Groups 1 and 2). A comparison of the ACAM2000[®] vaccination phase will also be presented between Groups 1 and 2.

Repeat assessments/measurements and unscheduled assessments/measurements will be included in the Individual Subject Data Listing. All other repeat values will be listed in a separate listing.

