### Questions:

The following specific cardiac questions will be routinely asked to the subject at the trial visits on the day of each vaccination; and the trial visits 2 weeks following each vaccination (Visits 3, 6

and 9 for Group 1; Visit 3 for Group 2) and 4 weeks following each vaccination (Visits 4, 7 and 10 for Group 1; Visit 4 for Group 2).

- Since your last visit, have you developed any chest pain, pressure, or discomfort that is beyond what is usual for you?
- Since your last visit, have you developed any shortness of breath at rest or exertion that is beyond what is usual for you?
- Since your last visit, have you noticed any swelling of your ankles, feet, or legs that is beyond what is usual for you?

If the answer to one of the question is "yes", further evaluations as outlined in [Figure 1](#) are initiated.

[figure not shown]
Subjects who develop any kind of cardiac signs or symptoms during the trial such as, but not limited to chest pain, dyspnea, arrhythmia or edema are referred to a local cardiologist for cardiac evaluation as described in the DoD Clinical Guidelines for Post-Smallpox Vaccine Associated Myopericarditis ([Appendix II; Section 17.2](#)). All treatment emergent AESIs will be followed up until complete resolution or until the sequelae are stable and considered to be permanent.

In any case of cardiac signs or symptoms, or increased laboratory results for Troponin I, the subject will be asked to attend for an unscheduled visit at the site, in order to perform or repeat Troponin I testing, to perform a physical examination for cardiac symptoms and to record an unscheduled ECG.

Further details regarding the follow-up of AESIs are described in the 'Investigator's Manual – Follow-up of Adverse Events of Special Interest'.

[Figure 1](#) outlines the algorithm for assessment of cardiac events.

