## 8.2.8 Safety Laboratory Measurements

The intensity of laboratory / systemic quantitatively measured toxicities will be graded according to the toxicity scale in [Appendix I; Section 17.1](#). These grading scales include the laboratory values determined with the routine safety parameters. In case of other laboratory values not included in the routine safety laboratory and not listed in [Appendix I; Section 17.1](#), the [National Cancer Institute Common Toxicity Criteria Table, Version 4.03, published June 14, 2010](#) will be used for grading of laboratory toxicities.

Safety laboratory (hematology and serum chemistry) is determined at the Screening Visit and Visit 3 for all subjects and at Visit 6 and Visit 9 for Group 1 only. If clinically indicated Safety laboratory tests can be performed at any other visit(s). The safety laboratory measurements are performed at the site specific local laboratory. Laboratory normal ranges are provided by the local laboratory and filed in the Regulatory File. Safety laboratory parameters to be evaluated are:

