### 5.1.3 Myocarditis and Pericarditis in the ACAM2000 Clinical Trial Experience

In clinical trials involving 2983 subjects who received ACAM2000 and 868 subjects who received Dryvax®, ten (10) cases of suspected myocarditis [0.2% (7 of 2983) ACAM2000 subjects and 0.3% (3 of 868) Dryvax® subjects] were identified. The mean time to onset of suspected myocarditis and/or pericarditis from vaccination was 11 days, with a range of 9 to 20 days. All subjects who experienced these cardiac events were naïve to vaccinia. Of the 10 subjects, 2 were hospitalized. None of the remaining 8 cases required hospitalization or treatment with medication. Of the 10 cases, 8 were sub-clinical and were detected only by ECG abnormalities with or without associated elevations of cardiac troponin I. All cases resolved by 9 months, with the exception of one female subject in the Dryvax® group, who had persistent borderline abnormal left ventricular ejection fraction on echocardiogram. The best estimate of risk for myocarditis and pericarditis is derived from the Phase 3 ACAM2000 clinical trials where there was active monitoring for potential of myocarditis and pericarditis. Among vaccinees naïve to vaccinia, 8 cases of suspected myocarditis and pericarditis were identified across both treatment groups, for a total incidence rate of 6.9 per 1000 vaccinees (8 of 1,162). The rate for the ACAM2000 treatment group were similar: 5.7 (95% CI: 1.9-13.3) per 1000 vaccinees (5 of 873 vaccinees) and for the Dryvax® group 10.4 (95% CI: 2.1-30.0) per 1000 vaccinees (3 of 289 vaccinees). No cases of myocarditis and/or pericarditis were identified in 1819 previously vaccinated subjects. The long-term outcome of myocarditis and pericarditis following ACAM2000 vaccination is currently unknown.

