3.10.10 Clinical Laboratory Variables (Hematology, Chemistry)

All measured hematology and chemistry values (and changes from baseline for continuous parameters) will be listed and summarized at each visit using descriptive statistics.

Summary tables will be produced for the number of high and low laboratory values at each visit by hematology and chemistry parameters.

In addition, all clinical laboratory values outside the normal range will be listed with screening number, demographic information and flagging of abnormal values (L = Below normal range, H = Above normal range) with their clinical significance.

'Shift tables' will be used to evaluate categorical changes from SCR to Visit 3, SCR to Visit 6 (Group 1 only) and SCR to Visit 9 (Group 1 only) with respect to normal ranges (below, within, above normal range) in hematology and chemistry parameters.

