3.10.11 Vital Signs and ECG

Measured vital signs values and changes from Baseline will be summarized at each time point using descriptive statistics. All measured values will be listed.

The investigator's overall interpretation of either normal, abnormal and if abnormal whether the ECG is clinically significant or not clinically significant, will be summarized at Screening and Visit 3. All ECGs including those clinically indicated and those not clinically indicated will be listed. In addition shift tables between SCR and Visit 3 and between SCR and Visit 9 (Group 1 only) will be produced to summarize the number of changes in ECG status.

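### The specified laboratory and ECG tables make no place for unscheduled or repeat values and have no toxicity-grade or worst-value summary, so findings below the AE and AESI thresholds and unscheduled peaks are assured only of a listing

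*SAP*

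**What the plan says.** SAP 3.10.1 gives one rule for measurements taken outside the schedule: "Repeat assessments/measurements and unscheduled assessments/measurements will be included in the Individual Subject Data Listing". Other repeat values go to a separate listing, and tables are organised by scheduled visit.

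For laboratory data, SAP 3.10.10 plans descriptive statistics by visit and then: "Summary tables will be produced for the number of high and low laboratory values at each visit by hematology and chemistry parameters". Shift tables run from screening to Visit 3 and, in Group 1, to Visits 6 and 9, "with respect to normal ranges (below, within, above normal range) in hematology and chemistry parameters".

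For ECGs, SAP 3.10.11 summarises the investigator's interpretation at screening and Visit 3. It adds: "In addition shift tables between SCR and Visit 3 and between SCR and Visit 9 (Group 1 only) will be produced". Clinically indicated ECGs are listed.

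The protocol asks for more than this captures. Section 8.2.8 says: "The intensity of laboratory / systemic quantitatively measured toxicities will be graded according to the toxicity scale in" Appendix I. Under section 8.2.7, after any cardiac sign or symptom or a raised troponin I, "the subject will be asked to attend for an unscheduled visit at the site, in order to perform or repeat Troponin I testing", with an unscheduled ECG as well.

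**The concern.** Unscheduled measurements are not a random sample. In this trial they are taken because a symptom or an earlier result raised suspicion, so they are among the most informative cardiac values collected. If the tables use only fixed visits, those values drop out of the tabulated comparison of the two vaccines, which is a stated secondary objective.

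Measured values matter here as well as event counts. The ACAM2000 label (Appendix IVc, 5.1.3) reports that 8 of 10 suspected myocarditis cases were sub-clinical, found only by ECG with or without a troponin rise. Appendix III, for a probable case, asks alongside symptoms for an abnormal troponin and does not set the bar at 2 x ULN.

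The second weakness is resolution. The trial grades laboratory values, but the shift tables see only below, within and above normal. Worsening within the abnormal range is invisible there.

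**Working it through.** The plan states no figure to reproduce. The check follows each kind of value from the protocol's AE and AESI definitions to the SAP text and the table list in SAP 5.1.

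**Step 1. Where each value goes.** Inputs: protocol 8.1.3.1 (laboratory values that are Grade 3-4 or judged clinically significant are AEs); protocol 8.1.3.3 (any cardiac sign or symptom, a clinically significant ECG, or troponin I at or above 2 x ULN is an AESI); SAP 3.10.1 and 3.10.9 to 3.10.11.

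| Value | At a scheduled visit | Unscheduled or repeat |
|---|---|---|
| Laboratory Grade 3-4 or clinically significant | By-visit tables and AE tables | AE tables, as an event |
| Laboratory Grade 1-2, not judged significant | By-visit counts and shifts | Listing |
| Troponin I at or above 2 x ULN | By-visit tables and AESI or SAE tables | AESI or SAE tables, as an event |
| Troponin I above ULN but below 2 x ULN | By-visit high count | Listing |
| ECG clinically significant | ECG status tables and AESI or SAE tables | AESI or SAE tables, as an event |
| ECG abnormal, not clinically significant | ECG status tables | Listing |
| Peak numerical value | By-visit maximum | Listing |

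Three qualifications apply.
- The AE route is tabulated for onset within 28 days of a vaccination. AESIs and SAEs count to the end of follow-up.
- A serious AESI moves to the SAE analysis, so it may not appear in Table 15.3.2.3 (AESI cardiac follow-up).
- Tables 15.3.2.3 and 15.3.3.3.5 (troponin I abnormalities) are given by title only. Whether they take unscheduled values is not stated.

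**Step 2. The second MVA-BN dose.** Protocol 8.2.7 and SAP 3.9.2 schedule troponin I at screening, Visit 3 and, in Group 1, Visit 9. The Visit 6 ECG is done only if clinically indicated. The SAP's ECG summary and shifts use screening, Visit 3 and Visit 9. Between the second MVA-BN dose (Visit 4) and the ACAM2000 dose (Visit 7), no troponin is scheduled and no ECG table is specified. Any such result can be tabulated only as an AE, AESI or SAE, unless the two title-only tables take it in.

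**Step 3. Three-class shifts for liver tests.** Inclusion criterion 12 admits ALT and AST up to 1.5 x ULN. I take the Appendix I liver function row to cover both:
- Grade 1: above 1.0 to below 2.5 x ULN
- Grade 2: 2.5 to below 4 x ULN
- Grade 3: 4 x ULN or more

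A subject moving from 1.4 to 3.9 x ULN goes from Grade 1 to Grade 2. That is an AE only if judged clinically significant. The shift table records it as above to above, the same as no change. The by-visit maximum and change from baseline may show the extreme, but not how many subjects worsened by a grade.

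**Step 4. Table titles.** SAP 5.1 lists seven laboratory tables (15.3.3.3.1 to 15.3.3.3.7) and three ECG tables (15.3.3.1.1 to 15.3.3.1.3). None of these ten titles names a toxicity grade, a worst post-vaccination value or unscheduled data.

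**The case against.** The strongest reply is that the important findings already have a second route into tables. Grade 3-4 laboratory values, troponin I at or above 2 x ULN, clinically significant ECGs and any cardiac symptom are tabulated as events, and none of these definitions is tied to a scheduled visit. A subject called back for symptoms is an AESI whatever the later troponin shows. One called back for a raised scheduled troponin is already in the by-visit high count. Protocol 9.6 also promises a descriptive analysis of ECG abnormality categories. All of this stands. A reader might infer that the worst cardiac and laboratory values never reach a safety table, or that troponin between 1 and 2 x ULN is counted in no summary. The documents do not support either reading.

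It is also fair that SAP 3.10.1 does not say unscheduled values go only to the listing, and that SAP 3.10.10 speaks of all measured values being summarised at each visit. Exclusion is the natural reading, since no rule assigns an unscheduled value to a visit, but it is an inference.

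The liver example does not extend to troponin. Entry below 2 x ULN is at most Grade 1, and the next grade starts at 2 x ULN, which is automatically an AESI.

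Nor does the label support a large share of cardiac onsets falling after the single scheduled check at Days 13-15. It says: "The mean time to onset of suspected myocarditis and/or pericarditis from vaccination was 11 days, with a range of 9 to 20 days". Spreading onset evenly over Days 9-20 would put 5/12 = 42% after Day 15, but its mean would be (9 + 20)/2 = 14.5 days, not 11. An assumed exponential shape starting at Day 9 with mean 11 gives exp(-6.5/2) = 3.9%. In any case, a late silent case triggers no unscheduled visit, so better tabulation would not reveal it.

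What the reply leaves open is that the event route records that something happened, not how high a value went, and it passes over changes below its thresholds.

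**Conclusion.** The point holds in a limited form. Followed as written, the specified laboratory and ECG tables omit:
- unscheduled and repeat values below the AE and AESI thresholds;
- unscheduled peak values;
- troponin and ECG results after the second MVA-BN dose.

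They also cannot show Grade 1 to Grade 2 liver-test worsening in subjects who enter above normal. These values remain in the listings.

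The size cannot be put as a number, because the documents do not say how many unscheduled measurements are expected. The direction is clear: the tables can only understate mild and moderate abnormalities, in both groups. No co-primary endpoint, sample size or trial procedure is affected. The change should be made because comparative safety is a secondary objective and the data and grading scale already exist.

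The conclusion assumes that assignment to a listing, with no rule for tables, means absence from tables, and that Tables 15.3.2.3 and 15.3.3.3.5 do not silently include unscheduled values. If they do, the troponin part narrows. The liver-test part stands either way.

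**What to change.** In SAP 3.10.10 and 3.10.11 add, per vaccination period and using scheduled, unscheduled and repeat values:

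1. worst post-vaccination troponin I, hematology and chemistry by Appendix I grade;
2. a shift table from baseline grade to worst grade;
3. worst ECG category (normal; abnormal, not clinically significant; abnormal, clinically significant).

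Keep the by-visit tables as planned. State in the SAP that Tables 15.3.2.3 and 15.3.3.3.5 include unscheduled values.

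Working per vaccination period matters because Group 1 has three periods and Group 2 has one. A worst value over the whole trial would give Group 1 more chances to be abnormal.

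The cost is SAP wording and a few extra tables from data already collected, with no change to conduct. Abnormality counts will look slightly less favourable. Subjects with symptoms are sampled more often, so the worst-value tables should be read beside the by-visit ones.
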